4.2 Enrolled Set

All subjects who have signed an informed consent and some study procedures have begun will be included in the enrolled set.

4.3 Randomized Set

All subjects in the Screened Set for whom a randomization number has been assigned will be included in the randomized set.

4.4 Safety Set

All subjects who have taken at least 1 dose of investigational product will be included in the safety set.

4.5 Full Analysis Set

All subjects in the Safety Set who have at least 1 post-baseline (i.e., randomization) primary efficacy assessment will be included in the full analysis set.

4.6 Per-protocol Set

All subjects in the Full Analysis Set who complete scheduled primary assessments for 6 study weeks and who do not have pre-defined protocol deviations that may affect the primary efficacy endpoint will be included in the Per-protocol Set. Refer to Appendix 19.4 for the protocol deviations that exclude subjects from the Per-protocol Set.

4.7 Completer Set

All subjects in the Full Analysis Set who have completed the final scheduled primary assessment for the study will be included in the completer set.

4.8 Pharmacokinetic and Pharmacodynamic Set

All subjects in the Safety Set for whom the primary PK and PD data are considered sufficient and interpretable will be included in the pharmacokinetic and pharmacodynamic set.

Page 22

5. SUBJECT DISPOSITION

The number and percentage of subjects who have been randomized and included in each subject population set will be presented by treatment sequence and overall. The denominator for the percentage calculation will be the number of randomized subjects.

The number and percentage of subjects who prematurely discontinued during the study will be presented for each treatment sequence, treatment at time of discontinuation and overall for the Safety Set and Full Analysis Set. Primary reasons for premature discontinuation from the study as recorded on the termination page of the eCRF will be summarized (number and percentage) by treatment sequence and by treatment received at time of discontinuation for the Safety Set and Full Analysis Set.

Subject disposition, subjects completing and terminating the study, and study analysis sets will be listed by subject for all subjects in the Enrolled Set.

Subjects who are excluded from the Per-protocol Set will be listed for the Full Analysis Set. Deviations from Inclusion/Exclusion criteria will be listed for the Screened Set.

6. PROTOCOL VIOLATIONS AND DEVIATIONS

Protocol deviation is defined as a variation from processes or procedures defined in a protocol. Deviations usually do not preclude the overall evaluability of subject data for either efficacy or safety, and are often acknowledged and accepted in advance by the sponsor.

Major Protocol deviation (violation) is defined as a significant departure from processes or procedures that were required by the protocol. Violations often result in data that are not deemed evaluable for a per-protocol analysis, and may require that the subject(s) who violate the protocol be discontinued from the study.

A summary of the number and percentage of subjects in the Safety Set with major protocol deviations (violations) or minor deviations will be produced.

All protocol violation and deviation data will be listed for the subjects in the Safety Set.

7. DEMOGRAPHIC AND OTHER BASELINE CHARACTERISTICS

Demographic and baseline characteristics will be determined using the screening visit or last observation prior to the first dose of investigational product, whichever is later. Descriptive summaries of demographic and baseline characteristics will be presented by treatment sequence for the Safety Set, Full Analysis Set and Per-protocol Set.

Subject demographics including age, age group (<18 yrs, 18-<=64 yrs, and >=65 yrs), sex, race, ethnicity, weight, height, BMI, and use of prophylactic therapy with C1 INH at randomization use will be summarized by treatment sequence for the Safety Set,Full Analysis Set, and Perprotocol Set. Continuous variables will be summarized by descriptive statistics including number of subjects, mean, standard deviation (SD), median, minimum, and maximum. Categorical variables will be summarized by the number of subjects in each category and the percentage of subjects out of the total in the respective analysis set.

Height and weight will be used to calculate BMI using the formula below:

$$BMI = \frac{\text{weight [kg]}}{(\text{height [m]})^2}$$

A listing will be created to show all the demographics and baseline characteristics for all subjects in the Enrolled Set.

7.1 Medical History

A medical history will be taken at the screening visit. All medical history findings that have been present/active within the 5 years prior to enrollment or any relevant history beyond 5 years that is considered important by the investigator will be entered into the CRF regardless of clinical relevance or presence at study start. The number and percentage of subjects in each primary system organ class (SOC) and each preferred term (PT) will be summarized by treatment sequence, a total of crossover sequences, and a total of all sequences on Safety set and Full Analysis Set. Medical history findings will also be listed for all subjects in the Enrolled Set.

7.2 HAE History

The following information associated with HAE history will be recorded in the CRF at the screening visit (NOTE: the attack rate may be estimated based on subject or parent/caregiver recall as well as the subject's medical records):

- HAE Type (I or II)
- Estimated date of last angioedema (swelling) attack prior to the screening visit
- Any therapy received during the last 12 months for management of HAE
- Any use of prophylactic therapy with C1 INH or Androgens prior to screening
- Any long-term prevention at randomization
- Total number, typical locations and average overall duration (days), and average overall severity of angioedema attacks experienced:

17 Aug 2017

during the 3 consecutive months prior to the screening visit (all subjects)

and (if applicable)

during the 3 consecutive months prior to starting prophylactic therapy with C1 INH or androgens.

• Typical Visual Analogue Scale (VAS) score for the subject's angioedema attack pain: during the 3 consecutive months prior to the screening visit (all subjects)

and (if applicable)

during the 3 consecutive months prior to starting prophylactic therapy with C1 INH or androgens.

HAE history will be summarized by treatment sequence for the Safety Set and Full Analysis Set, and also be listed for all the subjects in the Enrolled Set.

8. EXTENT OF EXPOSURE AND TREATMENT COMPLIANCE

8.1 Exposure to Investigational Product

For all treated subjects, including the ones who had early termination, treatment exposure is the duration between the first dose date and last dose date in each treatment period. Average daily dose, total dose, total number of doses, total exposure, length of exposure to investigational product (<=1 wk, >1 - <=2 wk, >2 - <=5 wks, >5 - <=10 wks, >10 - <=14 wks, >14 - <=18 wks, >18 - <=24 wks, >24 - <=28 wks, >28 wks), and treatment compliance will be summarized by treatment for the Safety Set and Full Analysis Set.

A listing will be created by subject and treatment and will show the date and time of dose administration for each treatment given for the Safety Set.

8.2 Measurement of Treatment Compliance

Investigational product dosing compliance for a specified period is defined as the total volume of investigational product actually taken by a subject during that period divided by the volume of investigational product expected to be taken during the same period, multiplied by 100. Each complete dose of investigational product will consist of a total volume of 4 mL. For doses where the drug administration was not complete, the dose is the total volume administered. The volume expected to be taken for a specified period is calculated as the number of weeks in that period multiplied by 4ml and multiplied by the number of doses to be taken per week (twice weekly) during that period.

Descriptive statistics including the number of subjects, mean, standard deviation, median, minimum, and maximum will be presented for exposure to investigational product and compliance by treatment for the Safety Set and Full Analysis Set. The treatment compliance will be categorized and summarized as follow: < 85, >= 85 - < 100, >= 100 for the Safety Set and Full Analysis Set.

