4.4.4 Thrombotic or Thromboembolic Event

If a thrombotic/thromboembolic (T/TE) event occurs in any subject, no further enrollment will occur pending a complete review of all available data. Already enrolled subjects will continue with investigational product administration and study procedures. Following a safety review of the T/TE event, study enrollment may be restarted if the medical monitor determines that the event was unrelated or unlikely to be related to investigational product or other C1 inhibitors, which may have been administered for an angioedema attack. Unblinding of the randomization code for that subject may be required (see below).

If a T/TE event occurs in any subject, investigational product administration for that subject will be discontinued (in Germany) or interrupted (in other countries); however, other study procedures will continue, as clinically appropriate. Diagnosis and management of all suspected T/TE events should be per local standard of care; [Appendix 4](#) and [Appendix 5](#) present a suggested medical algorithm for diagnosis and management of such conditions. Investigators must also comply with all reporting and/or procedures for AEs/SAEs as indicated in the suggested algorithm. Following a complete medical review by the sponsor in conjunction with the investigator, and if determined safe to do so, dosing with investigational product may be resumed (in all countries except Germany) to complete a total of 28 doses in the treatment period that was interrupted. Study procedures, including PK/PD testing, will resume relative to dosing. If investigational product cannot be restarted within 30 days of the temporary interruption, the subject will be discontinued from treatment and will follow the schedule of assessments for early discontinuation ([Table 3](#)). If unblinding is required, a physician external to the study will review relevant safety information, including the subject's assigned treatment. The unblinded physician will relay his or her findings and recommendations to the medical monitor, exercising caution not to reveal the subject's randomization to anyone associated with the conduct of the study.

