6.5 Treatment Compliance

Investigational product will be administered either by study site personnel or a qualified home health professional or may occur under their direct supervision for subjects (or parent/legal guardian/caregiver) who elect to self-administer during Treatment Periods 1 and 2 (Section 6.2). Therefore, full subject compliance with treatment is expected in this study.

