- 15. Have received an investigational drug within 30 days prior to the first dose of investigational product in Treatment Period 1. (E10)
- 16. Have, as determined by the investigator and/or the sponsor's medical monitor, any surgical or medical condition that could interfere with the administration of investigational product or interpretation of study results. (E11)
- 17. Subject administered "damaged" IP (e.g., IP with unapproved temperature excursion)
- 18. Calculated study drug compliance of <85% among subjects whose treatment duration is at least 6 weeks in the treatment period.
- 19. Subject missed \geq 3 consecutive doses
- 20. Subject was randomized but did not receive study drug
- 21. Investigator did not complete a separate angioedema attack CRF for each attack based upon their review of the data in the subject eDiary.
- 22. Concomitant use of Use of C1 INH therapy (other study drug) for prophylaxis against angioedema attacks after randomization upto 1 wk FU period
- 23. Initiation of long term therapy (including IV C1-INH, Transexamic acid or androgen therapy) after randomization upto the last dose
- 24. Change in dose of hormonal contraceptive regimen or hormone replacement therapy (ie, estrogen/progestin containing products) after randomization

- 25. Study drug is restarted later than 30 days of the temporary interruption after a Thrombotic/Thrombo-embolic event
- 26. Accidental Unblinding
- 27. Subject receiving 3 or more consecutive doses of incorrect treatment assigned by IXRS
- 28. Study drug exposed to temperature excursion (deemed unusable by Shire) dispensed to subject with reported AEs being associated with the exposed drug in the opinion of the PI.

HRQoL STATISTICAL ANALYSIS PLAN

Protocol No.:	SHP616-300
Project No.:	0238-0431
Protocol Title:	A Phase 3, Randomized, Double-blind, Placebo- controlled, Two-period, Three-sequence, Partial Crossover Study to Evaluate the Efficacy and Safety of Subcutaneous Administration of 2000 IU of C1 Esterase Inhibitor [Human] Liquid for Injection for the Prevention of Angioedema Attacks in Adolescents and Adults with Hereditary Angioedema: Assessment of Health-related Quality of Life (HRQoL)
Drug:	SHP616, C1 esterase inhibitor [human] liquid for injection
Sponsor:	Shire Development LLC and International Affiliates [name]
Version No. and Date:	Version 0.6, Date 22 August 2017

Version No:	Document History Description of Update	Author(s)	Effective Date

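### SAP 8.2 derives expected volume from weeks rather than scheduled doses, so compliance is misstated under either duration the SAP writes down, and the 85% Per-protocol exclusion inherits the error

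*SAP*

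**What the plan says.** SAP 8.2 fixes the dose volume ("Each complete dose of investigational product will consist of a total volume of 4 mL") and builds the denominator from time: "The volume expected to be taken for a specified period is calculated as the number of weeks in that period multiplied by 4ml", multiplied again by two doses per week. It refers to a specified period but does not say how the weeks in it are counted.

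The SAP writes down two candidate durations:
- SAP 8.1: "treatment exposure is the duration between the first dose date and last dose date in each treatment period". SAP 17.5 likewise ties treatment duration to the last dose date.
- The planned period of 14 weeks, given as 98 days in SAP 10.5.2.

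The result is used twice. SAP 8.2 tabulates it ("The treatment compliance will be categorized and summarized as follow: < 85, >= 85 - < 100, >= 100"). SAP 19.4 item 18 excludes from the Per-protocol Set any subject with "Calculated study drug compliance of <85% among subjects whose treatment duration is at least 6 weeks in the treatment period". SAP 4.6 otherwise admits Full Analysis Set subjects "who complete scheduled primary assessments for 6 study weeks", provided they have no listed deviation. The key secondary analyses (SAP 10.2) and the clinical-response summary (SAP 10.4) are run in that set as well as in the Full Analysis Set.

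**The concern.** The numerator counts doses and the denominator counts time. The two agree only when the time span contains exactly as many half-weeks as there were doses due.

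A first-to-last-dose span does not. It covers one interval fewer than the number of doses, so the last dose enters the numerator while its interval is missing from the denominator. Doses skipped at the end also shorten the span, so they cost nothing.

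A fixed 14 weeks fails the other way. A subject who stops early is charged for doses that were never due.

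What is at stake is the credibility of the compliance table and the membership of the Per-protocol Set. One reading keeps some subjects whose true compliance is below 85%. The other removes subjects who missed nothing before stopping. Protocol 4.4.1 lists lack of efficacy and adverse events among the discontinuation reasons, so removals of the second kind may be related to outcome.

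**Working it through.** **Inputs.** Dose volume 4 mL and two doses per week (SAP 8.2). Dosing every 3 or 4 days for 14 weeks (SAP 2.1). Exclusion below 85% when treatment duration is at least 6 weeks (SAP 19.4 item 18).

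**The plan's own figure.** 14 weeks × 2 = 28 doses, which agrees with protocol 4.4.4 ("to complete a total of 28 doses in the treatment period that was interrupted"). 28 × 4 mL = 112 mL.

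**Formula.** Compliance = 100 × (doses taken × 4) / (weeks × 8). True compliance = 100 × doses taken / doses due.

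**Reading 1: weeks = first-to-last-dose days / 7.** Twenty-eight doses span 27 intervals. Alternating 3 and 4 days gives 94 or 95 days, with a midpoint of 27 × 3.5 = 94.5 days = 13.5 weeks, or 108 mL expected.

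| Doses taken | Span (days) | Expected (mL) | Score | True |
|---|---|---|---|---|
| 28 of 28 | 94 / 94.5 / 95 | 107.4 / 108.0 / 108.6 | 104.3% / 103.7% / 103.2% | 100% |
| 27 of 28, one interior dose missed | 94 / 94.5 / 95 | 107.4 / 108.0 / 108.6 | 100.5% / 100.0% / 99.5% | 96.4% |
| 26 of 28, last two omitted | 25 × 3.5 = 87.5 | 100.0 | 104/100 = 104.0% | 92.9% |
| 11 of 13, two interior doses missed | 12 × 3.5 = 42 | 48.0 | 44/48 = 91.7% | 84.6% |

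If one day is added to each span, 28 of 28 scores 103.2% (95 days) or 102.1% (96 days). The 11-of-13 case becomes 44/(43/7 × 8) = 44/49.1 = 89.5%. Both directions of error remain.

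**Reading 2: weeks = 14, expected 112 mL.** The 85% line is 0.85 × 28 = 23.8 doses.

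| All doses taken, stopped after | Score | First-to-last span | Item 18 |
|---|---|---|---|
| 12 doses | 42.9% | 38–39 days, under 6 weeks | not triggered on this duration |
| 13 doses | 46.4% | 42 days | excluded |
| 16 doses | 57.1% | about 52.5 days | excluded |
| 20 doses | 71.4% | about 66.5 days | excluded |
| 23 doses | 82.1% | 77 days | excluded |
| 24 doses | 85.7% | 80–81 days | kept |

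The range wrongly removed is therefore 13 to 23 doses. It becomes 12 to 23 if duration is counted in calendar study weeks rather than dose dates.

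**How many subjects.** SAP 2.1 and 2.5 plan 52 crossover subjects with 44 completing both periods, so 52 − 44 = 8 non-completers are allowed for. That bounds the planned number exposed to Reading 2; only those stopping within the 13-to-23-dose range of a period would be affected.

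**The case against.** The strongest reply is that the formula matches the schedule: applied to a full 14-week period it returns exactly 112 mL, and SAP 8.2 never cites the SAP 8.1 duration. A third reading, weeks on treatment up to discontinuation, would be sensible. SAP 10.1 already uses days on treatment for discontinuers in the attack rate, and item 18's own 6-week condition suggests that time treated was intended. This is fair, but SAP 8.2 does not say it. If time treated is taken to end at the last dose, as SAP 17.5 suggests, it becomes Reading 1.

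Item 19, which excludes subjects missing three or more consecutive doses, catches longer gaps but not one or two missed doses. SAP 8.1 also reports dose counts and lists every administration, so missed doses stay visible elsewhere. The category and the exclusion still rest on the percentage.

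Some stronger readings are not supported:
- That a missed dose is always filed at 100% or above. One interior miss scores 99.5–100.5% by calendar, and 98.4% on a 96-day count. Likewise 23 of 28 doses scores 85.6% at 94 days but 84.7% at 95.
- That a fixed 14 weeks removes everyone stopping between weeks 6 and 12. Both ends fail, as the second table shows.
- That restarts after a thrombotic event break the formula on any reading. Under 14 weeks, 28 doses give 112/112 = 100%. Under elapsed time the result depends on the gap: a 14-day extension gives 112/124 = 90.3%.
- That protocol 6.5 ("Therefore, full subject compliance with treatment is expected in this study") is part of the fault. It states an expectation and enters no calculation.

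**Conclusion.** The point holds in a limited form. The denominator is not tied to scheduled doses, and both durations that the SAP writes down give wrong figures. First-to-last-dose duration overstates a full course by about 3–4 percentage points (2–3 with an added day), overstates a course missing its last two doses by 104.0 − 92.9 = 11.1 points, and keeps an 11-of-13 subject who should fall below 85%. A fixed 14 weeks excludes fully compliant subjects who stop after 13 to 23 doses.

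The figures assume dosing on the 3- or 4-day schedule and complete 4 mL doses.

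The consequence is modest. The primary analysis uses the Full Analysis Set (SAP 10.1), study success rests on it alone (SAP 10.3), and the key secondary endpoints are also analysed there. What changes is the compliance table and the Per-protocol repeats. Even there, a subject who stops in period 1 has no within-subject ratio for key secondary endpoints 1 and 3 in any set, so Reading 2 bears on those endpoints only through subjects who stop in period 2. It should still be settled before unblinding, because the choice of reading decides who enters the Per-protocol Set.

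**What to change.** In SAP 8.2, define expected volume as 4 mL × the number of scheduled doses due in the period: 28 for subjects who complete it, and the doses due up to the discontinuation date for those who stop. Use this figure in both SAP 19.4 item 18 and the three-category compliance table.

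The cases above then score as they should: 28 of 28 = 100%; 27 of 28 = 96.4%; 26 of 28 = 92.9%; 11 of 13 = 84.6%, which triggers item 18; and a compliant subject stopping after 16 doses = 16/16 = 100%, who is kept.

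The cost is one sentence of SAP text and one derivation. Dose dates and administered volumes are already collected. Reported compliance will look slightly less favourable than under the first-to-last-dose reading. No change to protocol 6.5 is needed for this point.

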9. PRIOR AND CONCOMITANT MEDICATION

Prior and concomitant medications will be coded using the World Health Organization-Drug Dictionary (WHODRUG) Version June 2017.

Prior medications are defined as medications with start time prior to the time of investigational product administration.

Concomitant medications are defined as medications with a start times after the time of investigational product administration or medications with a start time prior to investigational product administration but continuing after treatment, and with a start time before the 1-month post-treatment visit, inclusive.

Medical/surgical procedures performed during the treatment (between the dates of the first dose and the 1-month post-treatment visit, inclusive) will be recorded on the CRF, along with the date, time, and reason for the procedure.

Prior medication usage will be summarized using the number and percentage of subjects receiving each medication by treatment sequence, a total of crossover sequences and a total of all sequences, by indications, level 1 of the Anatomic Therapeutic Chemical (ATC) classification system and preferred term (PT) within the Safety Set and Full Analysis Set. Multiple medication usage by a subject in the same preferred term category will be counted only once. Concomitant medication/procedure by treatment, indications, ATC level 1, and preferred term (PT) within the Safety Set and Full Analysis Set. For this summary, concomitant medications will be assigned to a treatment if they are recorded at least once within the period corresponding to that treatment. Medical/surgical procedures will be listed for the Safety Set.

All non-study medications taken during the study will be listed and flagged with prior, concomitant and post treatment (taken after the 1-month post-treatment visit, exclusive) medications for Safety Set. Medical/surgical procedures performed during the treatment (between the dates of the first dose and the 1-month post-treatment visit, inclusive) will also be listed for the Safety Set.

